9.4.7 Prior and Concomitant Therapy

Any medication (including over-the-counter medications) or therapy administered to the subject prior to the study (within 6 months of randomization) and during the study (starting at the date of informed consent) will be recorded on the Prior & Concomitant Medication eCRF or Non-Pharmacological Procedures eCRF. The investigator will record on the Adverse Event eCRF any AE for which the concomitant medication/therapy was administered. If the concomitant medication/therapy is being administered for a medical condition present at the time of entry into the study, the investigator will record the medical condition on the Medical History and Current Medical Condition eCRF.

Listings of prohibited and permitted drugs are provided in [Appendix 2](#) (Prohibited medications are presented in [Listing 1](#), [Listing 2](#), and [Listing 3](#). Medications that are permitted with restrictions are listed in [Listing 4](#), [Listing 5](#), and [Listing 6](#)).

The following agents are not permitted before randomization (specific time frames are shown below) and until the last visit during the treatment period: (revised per Amendment 01)

- a) Immunoglobulin therapy and biologic drugs are not permitted within 6 months before Screening and until the last visit during the treatment period (revised per Amendment 01)
- b) Systemic or ocular immunosuppressive or immunomodulatory drugs are not permitted for a period of 5 half-lives or 60 days (whichever is longer) before randomization and until the last visit during the treatment period (revised per Amendment 01)
- c) Moderate to strong inhibitors of carboxylesterase 2 (CES2) enzyme activity are not permitted for a period of 5 half-lives or 7 days (whichever is longer) before

randomization and until the last treatment visit. Simvastatin use is permitted only with QD evening administration.

- d) Live/live attenuated vaccines are not permitted within 3 months before randomization and until the last treatment visit (this does not apply to non-live/inactivated vaccines) (revised per Amendment 01)

Concomitant therapy with AChEI or memantine should only be allowed and/or acceptable for the region or country in which the study is being conducted and should follow the local standard of care for symptomatic treatment (revised per Amendment 01). Subjects who are taking AChEI or memantine will be required to be on a stable dose for at least 12 weeks before randomization. Initiation of therapy or changing dose of AChEIs or memantine during the study should not be undertaken unless, for each subject, disease progression reaches a clinically significant medical threshold that requires additional symptomatic treatment. Subjects who start on AChEI or memantine or change their dose during the Treatment Period will be permitted to continue in the study; however, subjects should not undertake cognitive assessments until they have been on a stable dose for at least 4 weeks.

Subjects who are taking other medications will be required to be on a stable dose for at least 4 weeks before randomization, except for medications which are administered as short courses (eg, up to 3 weeks unless discussed and agreed with Medical Monitor) of treatment (eg, anti-infectives, oral steroids) or which are to be used on a PRN basis. Concomitant medications (including benzodiazepines and opiates) which are used on a PRN basis and which are central nervous system (CNS) active and may affect cognitive function are not permitted during a period of 72 hours prior to cognitive testing.

For subjects who undergo an LP for collection of CSF: Subjects who are on anticoagulants may have a variable dose but should have stable anticoagulation control for at least 4 weeks before the LP procedure. Subjects may be required to stop their anticoagulant medication prior to CSF collection and then restart this medication after the LP procedure, as per local guidelines.

Either aspirin or clopidogrel (or any other antiplatelet drug which is not aspirin) is permitted in all subjects. Aspirin and clopidogrel (or any other antiplatelet drug which is not aspirin) in combination are also permitted but subjects who are on such a combination of antiplatelet drugs may be required to stop 1 or more of these antiplatelet drugs before the LP procedure and restart after the LP as per local guidelines.

Subjects who initiate treatment with drugs not intended for treatment of cognitive impairment during the study should continue in the study if in the opinion of the investigator this will not interfere with study procedures or subject safety and are not prohibited above. However, if such drugs may affect cognitive function, subjects should not undertake cognitive assessments until they have been on a stable dose for at least 4 weeks.

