7.1 Nonclinical and Clinical Safety Data

The toxicity of elenbecestat (E2609) has been evaluated in oral repeated-dose toxicology studies of up to 26 weeks duration in rats and 39 weeks in cynomolgus monkeys. Nonclinical findings of note include immunologic-related findings at 30 mg/kg and above in monkeys (including 1 cytomegalovirus-related death at 60 mg/kg). An additional completed monkey immunology study suggested that lymphocytes and lymphocyte subsets may be suitable markers to monitor potential immunotoxicity or immunomodulation by elenbecestat (E2609) in a clinical setting. Further details of the nonclinical data to date with elenbecestat (E2609) can be found in the Investigator's Brochure.

The clinical program to date includes 9 Phase 1 studies and 1 Phase 2 study: (revised per Amendment 01)

Study E2609-A001-001 (Study 001) was a randomized, double-blind and placebo-controlled, SAD study that investigated doses ranging from 5 to 800 mg in healthy adult subjects (aged 30 to 55 years) and elderly subjects (50 mg dose only, aged 65 to 85 years).

Study 002 was a randomized, double-blind and placebo-controlled multiple ascending dose (MAD) study in healthy male and female subjects aged 50 to 85 years. CSF was collected before and following the 14 days of dosing so as to assess the PK levels of elenbecestat (E2609) and the pharmacodynamic (PD) effects on BACE activity and A β levels.

Study E2609-A001-003 (Study 003) was a single-center, open label study in healthy subjects investigating the effects of drug-drug interactions by itraconazole, rifampin, and donepezil on the PK properties of elenbecestat (E2609). It also investigated the effects of elenbecestat (E2609) on the PK properties of digoxin. The clinical phase has been completed and reporting is in progress.

Study E2609-A001-004 (Study 004) was a single-center, randomized, double-blind, placebo- and active-controlled, single dose, 4-treatment crossover study to evaluate the effects of elenbecestat (E2609) on QTc interval in healthy subjects (thorough QT study). Two dose levels of elenbecestat (E2609) were evaluated in this study, including a 50 mg therapeutic dose and a 200 mg suprathreshold dose.

Study E2609-A001-005 was an open label, single-dose study to determine the metabolism and elimination of [14 C]E2609 in healthy male subjects (aged 18 to 55 years).

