lower doses of 50 to 100 mg also caused some reduction in CD4 lymphocyte counts by Day 15. Doses above 100 mg appeared to be associated with greater reductions in CD4 and CD8 lymphocyte counts, which occurred earlier in the treatment period compared with the effects of 25 to 100 mg doses. These effects on lymphocyte counts gradually resolved from Day 20 to Day 35, which were 6 and 21 days, respectively, after administration of the last dose of elenbecestat (E2609) on Day 14. Reductions in CD4 and CD8 lymphocyte counts at doses of 200 and 400 mg to a level close to or less than the lower limit of normal (LLN) could be associated with increased risk of developing relapse of orolabial herpes or other infections.

In Study 003, a drug-drug interaction study, PK results showed that itraconazole (a potent inhibitor of cytochrome P450 [CYP] 3A4 and carboxylesterase-2 [CES2]) caused a mild increase (by approximately 70%) of the area under the concentration \times time curve (AUC) of elenbecestat (E2609). Rifampin (a potent CYP3A4 inducer) caused a mild decrease (by approximately 20%) of the AUC of elenbecestat (E2609). Donepezil (a moderate CES2 inhibitor) caused a mild increase (by approximately 20%) of the AUC of elenbecestat (E2609) when coadministered with elenbecestat (E2609) but not when dosed at least 2 hours apart from elenbecestat (E2609). Elenbecestat (E2609) (which inhibits the P-glycoprotein 1 transporter) did not affect the PK properties of digoxin. Nonclinical studies also indicated that other CYP pathways apart from CYP3A4 would not be major pathways of metabolism of elenbecestat (E2609). Based on these results, it is not considered necessary to impose restrictions during elenbecestat (E2609) treatment on the use of concomitant medications that may be CYP3A4 inhibitors or other CYP enzymes inhibitors. Similarly, it was also not considered necessary to restrict the use of concomitant medications which are inducers of CYP450 enzymes. Given the results of study 003 moderate to strong CES2 enzyme inhibitors are not permitted for a period of 5 half-lives or 7 days (whichever is longer) before randomization and until the last treatment visit.

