However, simvastatin use is permitted only with once daily evening administration. Simvastatin use is recommended with night time administration as physiological studies showed that most cholesterol is synthesized when dietary intake is at its lowest. It is therefore expected that the PK interaction between elenbecestat (E2609) and simvastatin is minimized because simvastatin is thought to mainly inhibit CES2 in the intestine when E2609 will not be present as it will be administered in the morning.

Study 004, a thorough QT study, demonstrated that single doses of elenbecestat (E2609) up to the suprathreshold dose of 200 mg did not have any clinically meaningful impact on the QTcF, heart rate, PR, or QRS intervals. The results from the moxifloxacin arm of the study confirmed adequate assay sensitivity for the study to detect even a small effect on QTcF. There were no T wave morphology abnormalities observed. Although the exposure-QTc analysis of the plasma concentration and $\Delta\Delta$ QTcF (placebo-corrected change from baseline of QTcF) detected a small but statistically significant relationship, overall data confirmed that an effect of >10 ms could be excluded up to the 200 mg suprathreshold dose of elenbecestat (E2609). The effects of elenbecestat (E2609) on QTcF were comparable between subjects with the slow NAT2 genotype and those with the rapid/intermediate NAT2 genotype, whether at 50 or 200 mg elenbecestat (E2609). This indicated that the M5

metabolite, whose PK is strongly influenced by NAT2 genotype, did not contribute to the effects on QTcF.

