Study 006, a Japanese bridging study, demonstrated that overall PK and plasma PD, measured as percentage reduction in $A\beta(1-x)$ from baseline at a 50 mg dose, were comparable between Japanese and white subjects. As a result, no dose adjustment was necessary for dosing Japanese subjects. In addition, the overall PK results indicated that the elenbecestat (E2609) plasma exposures (C_{max} and AUCs) were proportional to the dose in Japanese subjects between the dose range of 5 to 200 mg. The PD effects in plasma, expressed as the maximum plasma $A\beta(1-x)$ absolute reduction from baseline (A_{max}) and the total response (absolute change from baseline in the plasma $A\beta(1-x)$ $AUAC_{(0-144h)}$) increased with increasing dose from 5 to 200 mg in Japanese subjects. The single oral doses of elenbecestat (E2609) were generally safe and well tolerated in healthy Japanese and white subjects. The AE profile in this study was comparable between Japanese and white subjects with a low incidence of TEAEs. There were no AEs of special interest or viral infections. There were no effects of elenbecestat (E2609) on clinical chemistry, hematology parameters, or vital signs in healthy Japanese and white subjects. There was no clinically meaningful effect on QTcF following administration of elenbecestat (E2609) doses up to 200 mg based on the high precision QT analysis that demonstrated that the upper bound of predicted 90% CI of change from baseline in QTcF was below 10 ms. The relationship between the elenbecestat (E2609) concentrations and QTcF effect was similar between Japanese and white subjects at the elenbecestat (E2609) dose of 50 mg.

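### Item (c) of section 9.4.7 bars moderate CES2 inhibitors without excepting donepezil, and Study 003's 2-hour spacing result never becomes a dosing instruction

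*Protocol*

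**What the plan says.** **The ban.** Section 7.1 bases it on Study 003: "Given the results of study 003 moderate to strong CES2 enzyme inhibitors are not permitted". Item (c) of 9.4.7 repeats it ("Moderate to strong inhibitors of carboxylesterase 2 (CES2) enzyme activity are not permitted for a period of 5 half-lives or 7 days"), and so does item (c) of the synopsis. The class includes moderate inhibitors. The one drug-specific allowance in item (c) and in the note under Listing 1 is simvastatin, once daily in the evening.

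**Donepezil's class and measured effect.** Section 7.1 reports from Study 003: "Donepezil (a moderate CES2 inhibitor) caused a mild increase (by approximately 20%) of the AUC of elenbecestat (E2609) when coadministered" with study drug, "but not when dosed at least 2 hours apart from elenbecestat (E2609".

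**Donepezil's permission.** Listing 4 in Appendix 2 names donepezil as a permitted cognitive enhancer. Inclusion criterion 6 admits AChEI users on a dose stable for 12 weeks. The AChEI paragraph of 9.4.7 also lets subjects start or change an AChEI after randomization. The conditions attached are stable dose, local standard of care and the timing of cognitive tests.

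**Timing of study drug.** Section 9.4.5 fixes a once-daily morning dose.

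**Why simvastatin is handled separately.** Section 7.1 reasons that its inhibition falls mainly in the gut at a time when the morning study drug is absent: "It is therefore expected that the PK interaction between elenbecestat (E2609) and simvastatin is minimized".

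**The concern.** Two things do not fit together.

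First, item (c) taken word for word covers a drug that Listing 4 permits. Because exclusion criterion 18 removes anyone on prohibited medication, the gap touches eligibility as well as conduct.

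Second, the protocol holds a measured result showing how to avoid the donepezil interaction and does not use it. A site that follows the permissive text exactly may let a subject take donepezil and study drug together every morning for up to 24 months. In the active arm that raises exposure to a drug with a known lymphocyte signal, where confirmed lymphocytopenia interrupts dosing (section 9.3.3).

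**Working it through.** No figure in the sample size or alpha plan is at issue, so there is none to reproduce. The check sets the text side by side, then scales the effect.

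**Step 1. Rules on CES2 and donepezil**

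| Place | Donepezil status | Spacing from study drug |
|---|---|---|
| 7.1 | moderate CES2 inhibitor; class barred | 2-hour result reported, no instruction |
| Synopsis (c), 9.4.7(c) | within the barred class; no exception | none |
| Listing 1 | not among the eight named drugs | none |
| Inclusion 6 | AChEI users eligible | none |
| 9.4.7, AChEI paragraph | allowed, including new starts | none |
| Listing 4 | named as permitted | none |
| 9.5.1.4.1 and Table 3 note u (PK days) | not mentioned | none |

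Absence from Listing 1 does not by itself exempt donepezil. Appendix 2 warns that its listings may be incomplete, and itraconazole, which 7.1 calls a potent CES2 inhibitor, is not in Listing 1 either.

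**Step 2. Compare with simvastatin.** Study 003 is described as testing itraconazole, rifampin and donepezil on study drug, and study drug on digoxin. Simvastatin is not among them, yet it has a timing rule so that CES2 inhibition and study drug do not coincide. Donepezil's interaction was measured and disappeared with spacing, yet it has no timing rule.

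**Step 3. Size per subject.**
- Inputs: dose 50 mg; AUC rise about 20% together, none at 2 hours or more (7.1).
- Formula: AUC-equivalent dose = dose × (1 + rise).
- Together: 50 × 1.20 = 60 mg. Spaced: 50 × 1.00 = 50 mg.
- Assumption: AUC proportional to dose. Section 7.1 reports for Study 006 that exposures "were proportional to the dose in Japanese subjects between the dose range of 5 to 200 mg". Those were single doses in healthy men, so the 60 mg figure is a rough guide only.

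For context, 7.1 says of the 14-day multiple-dose study that the "lower doses of 50 to 100 mg also caused some reduction in CD4 lymphocyte counts by Day 15", with greater reductions above 100 mg. Both 50 and 60 mg lie inside the lower band.

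**Step 4. Size across the active arm.** Let p be the share of active-arm subjects who take both drugs together. Assuming equal underlying AUC, the mean rise is 20% × p, so it runs from 0% (p = 0) to 20% (p = 1). The protocol gives nothing from which to estimate p.

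**Step 5. Effect on inference.** The sample size in 9.7.2 rests on a placebo mean change of 1.75, a 25% reduction, an SD of 2.05 and 30% dropout; none of these changes. Concurrent AD medication use (yes/no) is a stratum and a term in the primary model (9.7.1.6.1). The number of tests and the alpha level do not change.

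**The case against.** The strongest reply is that the protocol has already judged effects of this size acceptable. Section 7.1 calls the donepezil rise mild, and after a rifampin shift of about 20% in the other direction it sees no need to restrict CYP inducers. On that view a spacing rule is only a preference. This does not carry over. The relaxations in 7.1 are for CYP inhibitors and inducers. For CES2 the same section goes the other way and bars even moderate inhibitors, citing Study 003. Nowhere does it say that the donepezil effect was considered and accepted.

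A second reply is that simvastatin's interaction was not measured, so caution there and none for a measured mild effect can coexist; 7.1 also gives a lipid-synthesis reason for night dosing. That weakens the comparison but leaves the main gap: the remedy for donepezil is known and unused.

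Much of the rest of the case stands. A reader might infer from item (c) that donepezil users are actually barred. The documents do not support that. Section 9.4.7 points to Listing 4, the AChEI paragraph follows directly after the list of barred drugs, criterion 6 admits users, concurrent AD medication is a stratum, and starting an AChEI is an exploratory endpoint. The intent to allow donepezil is clear, and sites would probably decide correctly. Lymphocytes are monitored, with interruption and stopping rules, and nothing in the protocol shows that 60 mg differs from 50 mg in its effect on them.

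**Conclusion.** The point holds and is minor. The protocol bars a class, places donepezil in it, permits donepezil elsewhere, and leaves out both the exception and the spacing that its own data support. The consequence is a mild, avoidable rise in exposure of about 20% in AUC for active-arm subjects who take the two drugs together, and none for those who already separate them.

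Two stronger readings should be resisted. A reader might set the 20% against the AUC rise behind the moderate hepatic impairment exclusion. That comparison is unsound: the exclusion followed increases of about 91% in Cmax and 45% in AUC together, and no Cmax effect is given for donepezil. A reader might also infer bias in the efficacy result. Nothing in the protocol supports that; the primary comparison, type I error and sample size are untouched.

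The conclusion rests on the text available, Version 2.0 and the Version 1.0 text in the same file, which agree on this point. A later amendment could have changed it.

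**What to change.** In synopsis item (c), 9.4.7(c) and the note under Listing 1, add: donepezil is permitted per Listing 4 and should be taken at least 2 hours apart from study drug, including when started after randomization. Apply it in both arms, and leave the time of day otherwise to local standard of care. On PK days, when study drug is taken at the clinic after the predose sample, the 2 hours should be counted from that dose. As an option, the existing telephone contact before PK visits (Table 3 note u) could also record the donepezil dose time.

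The cost is one sentence in three places at the next amendment and a small dosing-time burden. Some subjects on a settled donepezil routine would have to move their dose time. The dose itself does not change, so the 12-week stability requirement is still met. No extra subjects, visits or samples are needed.

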9.3.3 Removal of Subjects from Therapy or Assessment

The investigator may withdraw the subject from the study at any time for safety or administrative reasons. The subject may stop study drug or withdraw from the study at any time for any reason.

Absolute lymphocyte count from the hematology and differential panel will be monitored during the study. ALC will be derived from the CBC with differential representing the normal lymphocytes (with atypical lymphocytes removed and presented as a separate count if they are present) and calculated by the white blood cell count \times percentage of lymphocytes. (revised per Amendment 01) Should a subject develop a Grade 2 or greater lymphocytopenia (less than $800/\text{mm}^3$), this should be confirmed as soon as possible but no later than within 5 days with a repeat test of absolute lymphocyte count. If confirmed, study drug administration should be interrupted for a minimum period of 2 weeks and for a maximum period of 4 weeks. Restart of study drug may take place only when absolute lymphocyte count returns to greater than LLN. Absolute lymphocyte count will be measured 4 weeks after restart of study drug. Subsequent measurements of absolute lymphocyte counts will follow the schedule of assessments (Table 3) and any results showing a Grade 2 or greater lymphocytopenia (less than $800/\text{mm}^3$) should be handled as above. If a 2nd occurrence of Grade 2 or greater lymphocytopenia (less than $800/\text{mm}^3$), that is confirmed on repeat testing, occurs within 6 months, then the subject should be discontinued permanently from the study drug.

Subjects who develop moderate or severe hepatic impairment during the study must discontinue study drug. (revised per Amendment 01)

Subjects who discontinue study drug early must complete the ED Visit (within 7 days of the last dose of study drug) and the Follow-Up Visits (1 and 3 months after the last dose of study drug). These Follow-Up Visits will be conducted to monitor efficacy and safety parameters after early withdrawal from the study or discontinuation of study drug.

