The following adverse events will require the collection of information sufficient to provide a detailed description of the event, treatment, and outcome to the Medical Monitor for the study: any treatment-emergent significant laboratory abnormality; any seizures, herpes zoster infection, severe infection; any moderate to severe drug rash or any rash lasting more than 72 hours (regardless of severity); amyloid-related imaging abnormalities (cerebral vasogenic edema, macrohemorrhage, an area of superficial siderosis, or a new microhemorrhage); a positive suicidality assessment on either the C-SSRS or the clinical assessment of suicidality

All AEs must be followed for 12 weeks after the subject's last dose, or until resolution, whichever comes first. Subjects who have a Grade 2 or greater lymphocytopenia (less than $800/\text{mm}^3$) during the follow-up period (ie, at either Visit 14 or Visit 15) should have ALC measured every 4 weeks until resolution or confirmation of a non drug-related cause of the lymphocytopenia. ALC will be derived from the CBC with differential representing the normal lymphocytes (with atypical lymphocytes removed and presented as a separate count if they are present) and calculated by the white blood cell count \times percentage of lymphocytes. (revised per Amendment 01) All SAEs must be followed to resolution or, if resolution is unlikely, to stabilization.

Every effort must be made by the investigator to categorize each AE according to its severity and its relationship to the study treatment.

Assessing Severity of AEs

AEs will be graded on a 3-point scale (mild, moderate, severe) and reported in the detail indicated on the eCRF. The definitions are as follows:

Mild	Discomfort noticed, but no disruption of normal daily activity
Moderate	Discomfort sufficient to reduce or affect normal daily activity
Severe	Incapacitating, with inability to work or to perform normal daily activity

The criteria for assessing severity are different than those used for seriousness (see [Section 9.5.1.5.2](#) for the definition of an SAE).

Assessing Relationship to Study Treatment

Items to be considered when assessing the relationship of an AE to the study treatment are:

- Temporal relationship of the onset of the event to the initiation of the study treatment
- The course of the event, especially the effect of discontinuation of study treatment or reintroduction of study treatment, as applicable

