Immune globulin IV, IVIG, IGIV	Carimune, Flebogamma, Gamimune N, Gammagard, Gamunex, Gammar-P IV, Iveegam, Octagam, Panglobulin, Vigam, Polygam S/D, Privigen, Sandoglobulin, Venoglobulin-S
Denosumab	Prolia (revised per Amendment 01)
Other monoclonal antibodies not listed here	

^aTopical and inhaled formulations with minimal systemic exposure need not be prohibited.

Listing 3 Prohibited Live/Live Attenuated Vaccines Within 3 Months Before Randomization and Until the Last Visit During the Treatment Period (this does not apply to non-live/inactivated vaccines)

Bacterial vaccines	Viral vaccines
Bacillus Calmette-Guérin vaccine against tuberculosis	Measles vaccination
Typhoid vaccination (oral)	Mumps vaccination
Cholera vaccination (oral)	Rubella vaccination
	Oral polio vaccination (Sabin)
	Yellow fever vaccination
	Varicella (chickenpox) vaccination
	Rotavirus vaccination
	Japanese encephalitis vaccination
	Live attenuated influenza vaccine (FluMist in the United States and Canada, and Fluenz in Europe)

This list is not exhaustive

Permitted Prior/Concomitant Medications

Listing 4 Medications Which Need To Be on a Stable Dose for 12 Weeks Before the Cognitive Assessments at Visit 2 and Should Remain on the Same Stable Dose From Visit 2 to Follow Up Visit 15

Cognitive Enhancers	
Donepezil	Aricept
Rivastigmine	Exelon
Galantamine	Reminyl
Memantine	Namenda

Listing 5 Permitted Medications Used on PRN Basis Which are not to be Used Within 72 Hours Before Cognitive Testing

Generic name	Trade name
Opiates	
Morphine	Astramorph PF, Avinza, Depo Dur, Duramorph, Infumorph, Kadian, MS Contin, MSIR, Oramorph SR, RMS, Roxanol
Opiate Agonists	
Meperidine	Demerol, Meperitab
Fentanyl	Actiq, Duragesic, Fentora, Onsolis, Sublimaze
Codeine	Codeine
Oxycodone	Dazidox, Endocodone, Eth-OxyDose, OxyContin, OxyFast, OxyIR, Percolone, Roxicodone, Roxicodone Intensol
Other opioids or opioid agonists which are used on PRN basis	
Benzodiazepines and sedatives	
Estazolam	ProSom
Alprazolam	Alprazolam Intensol, Niravam, Xanax
Triazolam	Halcion
Midazolam	Versed
Lorazepam	Ativan
Flunitrazepam	Rohypnol
Temazepam	Restoril
Clonazepam	Ceberclon, Klonopin
Diazepam	Diastat, Dizac, Valium
Chlordiazepoxide	H-Tran, Librium
Flurazepam	Dalmane
Zopiclone	(various)
Zolpidem	Ambien; others
Ramelteon	Rozerem
Amitriptyline	(various)
Dothiepin	(various)
Risperidone	Risperdal
Olanzapine	Zyprexa
Promethazine	Phenergan; others

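### The live-vaccine ban ends on the day of the last dose for completers; as a low-cost precaution it should run to Follow-Up Visit 14

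*Protocol*

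**What the plan says.** The end of the ban is stated consistently in three places of the amended protocol.

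- Section 9.4.7(d), repeated in the synopsis under Concomitant Drug/Therapy: "Live/live attenuated vaccines are not permitted within 3 months before randomization and until the last treatment visit".
- The lead-in to the list in both places: "The following agents are not permitted before randomization (specific time frames are shown below) and until the last visit during the treatment period".
- Appendix 2, heading of Listing 3: "Prohibited Live/Live Attenuated Vaccines Within 3 Months Before Randomization and Until the Last Visit During the Treatment Period".

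The safety background is in Section 7.1. In the multiple-ascending-dose study, "lower doses of 50 to 100 mg also caused some reduction in CD4 lymphocyte counts by Day 15". On recovery it says: "These effects on lymphocyte counts gradually resolved from Day 20 to Day 35, which were 6 and 21 days, respectively", counted from the last dose on Day 14. The link to infection risk is made for reductions in CD4 and CD8 "counts at doses of 200 and 400 mg to a level close to or less than the lower limit of normal (LLN").

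Two other rules bear on the point. Under Section 9.3.3, if a second confirmed absolute lymphocyte count (ALC) below 800/mm3 "occurs within 6 months, then the subject should be discontinued permanently from the study drug". Under Section 9.5.1.5.1, a subject with a count that low "during the follow-up period (ie, at either Visit 14 or Visit 15") is retested every 4 weeks until it resolves or a cause other than the drug is confirmed. Neither rule mentions vaccination.

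**The concern.** A live-vaccine ban in a trial of a drug that may lower lymphocyte subsets protects the subject while that effect lasts. Here the ban starts 3 months before randomization but has no tail after the last dose, although the protocol's own safety summary describes effects that took time to resolve once dosing stopped. A completer could receive a live vaccine the day after Visit 13 without breaking any rule.

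What is at stake is patient safety only. The efficacy analysis, the type I error and the power are untouched.

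**Working it through.** **Inputs**

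- Last dose in the multiple-ascending-dose study: Day 14. Resolution: gradual, from Day 20 to Day 35 (Section 7.1).
- Visit 13: Day 729. Visit 14: Day 757. Window for follow-up visits: ±3 days (Table 3 and footnote a).
- Dosing at Visit 13: in the clinic, with a PK sample 4 to 8 hours after the dose (Table 3, footnotes v and x).
- ED Visit: within 7 days of the last dose (Table 3, footnote b).
- Visits 14 and 15: 4 and 12 weeks after the last dose for all subjects, and called post-treatment for early stoppers too (Section 9.1.2.2).
- Length of the Treatment Period: 24 months (Section 9.1).

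**Step 1: the protocol's recovery figures.** 20 − 14 = 6 days and 35 − 14 = 21 days. Both agree with Section 7.1. They mark the start and end of a period of gradual resolution, so the figure for when the reported effects had resolved is 21 days.

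**Step 2: completers.** Visit 14 is set at 4 weeks after the last dose, and 757 − 28 = 729, which is Visit 13. The last dose and the end of the ban therefore fall on the same day. Post-dose cover is 0 days, so none of the 21 days is covered (21 − 0 = 21).

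**Step 3: early stoppers.** There are two readings.

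- If the ban ends at the ED Visit, cover is 0 to 7 days, which leaves 21 − 7 = 14 to 21 − 0 = 21 days of the reported interval uncovered. This is the more natural reading, because the visits after ED are called post-treatment.
- If the ban ends at month 24, because the Treatment Period is defined as 24 months, a subject who stopped at least 21 days before that point is covered for the whole interval.

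The text does not choose between them. The gap for completers exists under either.

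**Step 4: would Visit 14 be late enough?** 757 − 729 = 28 days after the last dose, or 25 to 31 days with the ±3-day window. That passes 21 days by 28 − 21 = 7 days, and by 4 to 10 days across the window.

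**Step 5: does a 4-week tail fit the rest of the protocol?** Yes. Treatment-emergent adverse events are counted to 4 weeks after the last dose (Section 9.7.1.8.2), contraception continues for 28 days after discontinuation (Section 9.3.2), and hematology is already drawn at Visits 14 and 15 (Table 3).

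**The case against.** The best defence is that the end date was chosen, not overlooked. The revision history shows that Amendment 01 reviewed these time frames, the three places agree with each other, and where the sponsor wanted a post-dose tail (contraception) it wrote one. The evidence at the trial dose is also thin: only some CD4 reduction at 50 to 100 mg, with infection risk tied to 200 and 400 mg. Safeguards exist as well. Subjects enter with ALC at or above both the lower limit of normal and 800/mm3, hematology is drawn at every visit, dosing stops for a confirmed low count and resumes only above the lower limit of normal, and Section 9.5.7 has the investigator ask about care planned elsewhere. Completers who enter the extension will fall under rules still to be written.

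Most of this stands and is why the point is rated low. It does not close the gap. None of the safeguards restricts vaccination, and nothing in the protocol supports zero days of cover after 24 months of exposure.

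A reader might infer more than the documents support:

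- **That subjects on 50 mg leave treatment with counts near or below normal limits.** Section 7.1 describes that only for 200 and 400 mg.
- **That 21 days bounds recovery in this trial.** It comes from 14 days of dosing, is not broken down by dose, and says nothing about 24 months at 50 mg.
- **That as little as 6 days, or none, would be uncovered.** Day 20 is where gradual resolution began to be seen, not a time of full recovery.
- **That the number affected follows from the assumed 30% dropout.** Dropout in the sample-size section is not study-drug discontinuation; early stoppers may stay on study. No frequency of lymphopenia or of live vaccination is given.
- **That a subject stopped permanently for a repeated low count is certainly released at the ED Visit.** That depends on the unsettled reading in step 3.

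**Conclusion.** The point holds as a precaution of low severity. Completers have no live-vaccine cover after the last dose. Early stoppers have 0 to 7 days if the ban ends at the ED Visit, and the text should say whether it does. Set against the only recovery interval that the protocol reports, 21 days are uncovered for completers and 14 to 21 days for early stoppers on the ED reading.

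These figures assume that an interval seen after 14 daily doses, over a range of doses, is a usable guide to 50 mg after 24 months. The protocol neither confirms nor excludes that, so the figures show why a tail is sensible and do not measure the risk. The present text is consistent and contradicts nothing. The case for change is that the protection is nearly free.

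**What to change.** - In Section 9.4.7(d), the matching synopsis item and the heading of Listing 3, end the live/live attenuated vaccine ban at Follow-Up Visit 14 (4 weeks after the last dose), and state that this applies after early discontinuation too.
- In the lead-ins of Section 9.4.7 and the synopsis, add an exception for item (d), so that they do not contradict the new end date.
- If ALC is below 800/mm3 at Visit 14, continue the restriction. If it is first found below 800/mm3 at Visit 15, reinstate it, because by then the ban will have lapsed. In both cases keep it until resolution or a confirmed cause other than the drug, as Section 9.5.1.5.1 already does for retesting. Total ALC is an imperfect stand-in for the CD4 and CD8 effects in Section 7.1, but it is the count for which the protocol already has a threshold and a follow-up rule.
- Leave the other bans unchanged. Extending them could obstruct ordinary care, such as treatment of a rash that led to discontinuation.

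The cost is wording in five places, with no new visit or test. Because the trial is blinded, the rule applies to both arms: elective live vaccination is deferred by about 4 weeks, and longer only where a low ALC persists. Inactivated vaccines are unaffected.
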